7.4 Analysis of the Primary Endpoint

The number and percentage of subjects with 12-month TLF will be provided. A one-sided upper 95% confidence interval of the Resolute Onyx 2.0 mm stent 12-month TLF rate will be calculated through binomial (exact) method. If this upper limit is below 19%, the clinical objective will be considered to have been met.

With regard to clinical outcomes analysis, in subjects receiving treatment of two lesions with a Resolute Onyx 2.0 mm stent, the lesion to be included in the primary analysis, the “analysis lesion”, will be randomly selected at the time of analysis. For subjects receiving treatment of a Resolute Onyx 2.0 mm stent and another size stent, the primary analysis will include the lesion treated with the 2.0 mm stent, regardless of the other stent size. A secondary analysis will be conducted for all target lesions.

Statistical non-significance in the primary endpoint for gender comparisons will confirm the homogeneity by gender in this trial.

7.5 Analysis of the Secondary Endpoints

Descriptive statistics for the secondary endpoints will be provided. Categorical variables will be reported using counts and percentages, and continuous variables will be reported by giving the number of known values, the mean, standard deviation, minimum and maximum values. The time-sensitive nature of any response variable may be displayed by using a Kaplan-Meier plot.

7.6 Analysis of Baseline Characteristics

All clinically relevant baseline variables will be tabulated and reported. Categorical variables will be reported using counts and percentages, and continuous variables will be reported by giving the number of known values, the mean, standard deviation, minimum and maximum values.

7.7 Endpoint Analysis and Reporting of Results

All statistical analyses will be performed using SAS for Windows (version 9.1 or higher) or other widely accepted statistical or graphical software. Subject data listings and tabular and graphical presentations of results will be provided.

7.8 Missing Data

Every effort will be undertaken to minimize missing data. In time-to-event outcomes drop-outs will be censored at the time of discontinuation, consistent with the Kaplan-Meier approach.

RESOLUTE Onyx 2.0 mm Clinical Study**CONFIDENTIAL - May not be reproduced without written permission from Medtronic**

Unless otherwise specified, no statistical techniques will be used to impute missing data for continuous or categorical outcomes. The number of subjects included in each analysis will be reported so that the reader can assess the potential impact of missing data.

For the primary endpoint, a sensitivity analysis will be conducted to assess the impact of censored data and will include a worst-case analysis.

8.0 CLINICAL EVENTS

8.1 Adverse Events

8.1.1 Definition

An adverse event (AE) is any untoward medical occurrence, unintended disease or injury, or untoward clinical signs (including abnormal laboratory findings) in subjects, users or other persons, whether or not related to the investigational medical device.

Note 1. This definition includes events related to the investigational medical device or the comparator.

Note 2. This definition includes events related to the procedures involved..

Note 3. For users or other persons, this definition is restricted to events related to investigational medical devices.

A device related AE is defined as any AE for which a causal relationship between the event and the device implantation procedure, the presence of the device, or the performance of the device system, is at least a reasonable possibility (i.e., the relationship cannot be excluded).

A procedure related AE is as any AE associated with the initial placement of the device or any necessary secondary interventions. This includes morbidity associated with either anesthesia or the procedure. This also includes inappropriate subject selection and errors attributed to inappropriate operator techniques, measurements, or judgment.

8.1.2 Reporting Requirements

All non-serious AEs occurring from the time of index procedure through 12 months post-procedure will be recorded in the subject's medical record and reported on the adverse event eCRF within 10 working days after the designated study site personnel first learns of the event. A list of AEs that may be associated with the use of the study device and/or the interventional procedure is provided in the IFU. Each AE must be evaluated to determine if the event meets the definition of serious adverse event (see [Section 35](#)). Event, date of onset, duration, and relationship to device will be recorded on the eCRF. AEs will be followed until the event has resolved (in the case of permanent impairment, the event will be followed until it stabilizes and the overall clinical outcome has been ascertained). The AEs must also be reported to the IRB per the institution's policy for reporting AEs.

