1.7 Schedule of Follow up Assessments

Subject Contact (the subject will be assessed by telephone, e-mail, and/or office visit) at:

- 30 days
- 6 months (subjects that did not have baseline MPI performed)
- Annually 12 months, 2 and 3 years (all subjects)

Clinic Visit (the subject must return to the same investigational site where the index procedure was performed) at:

- 6 months (MPI assessment – subjects with baseline MPI performed and consent to follow-up MPI only)
- 13 Months (angiographic assessment – 2.0 mm Angio subset subjects only)

RESOLUTE Onyx 2.0 mm Clinical Study**CONFIDENTIAL - May not be reproduced without written permission from Medtronic**

- Angiography should be performed for any post-procedure clinical event (e.g., MI) to determine if the event is attributable to the target vessel or a non-target vessel. The reason for any repeat angiography (either clinically driven or non-clinically driven) must be documented on the CRF.

Revascularization should only be conducted when ischemic symptoms are found by an objective measurement and stenosis alone does not justify revascularization.

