4.0 CLINICAL TRIAL DESIGN

The Medtronic RESOLUTE ONYX 2.0 mm Clinical Trial is a single arm, open label, multi-center trial enrolling at least 100 subjects with ischemic heart disease attributable to stenotic lesions of the native coronary arteries that are amenable to percutaneous treatment with a Resolute Onyx 2.0 mm stent. At least 20 subjects will be enrolled to receive an angiographic follow up at 13 months.

Subjects may receive treatment of one or two lesions, one lesion per target vessel, for a maximum of two target vessels. Only one lesion may be treated in a single target vessel. All treatment with the study stents is to be performed during a single index procedure. Refer to [Table 2](#) for additional stenting criteria.

In the event of one lesion to be treated with a 2.0 mm study stent and another lesion to be treated with a core size (2.25 mm - 4.0 mm) Resolute Integrity stent, the subject should be treated first with the core-sized stent. If the treatment of the first lesion fails or if the subject becomes unstable *before* a 2.0 mm study stent is attempted (stent introduced into guide catheter), the subject will not be enrolled, will not be followed, and will not be included in the primary analysis of this trial. Another subject should be enrolled to replace this subject for the primary analysis. If the treatment with the 2.0 mm study stent is attempted (stent introduced into guide catheter) but not implanted, the subject will be considered part of the Intention-to-Treat population (ITT) and will be followed through the 12 month endpoint and will be included in the primary analysis of this trial.

For subjects who have more than one lesion planned for treatment, a positive functional study or FFR should be performed in the vessel expected to receive the 2.0 mm study stent to demonstrate the functional need for treating such a lesion.

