5.2 Clinical Laboratory Procedures & Tests

The clinical procedures that must be performed and laboratory tests that must be drawn for all subjects prior to the stenting procedure are listed below and in [Table 3](#). The results for the procedures and tests required to assess subject eligibility for enrollment (white blood cell (WBC) count, platelet count, creatinine, creatine kinase (CK), Troponin, ECG and pregnancy test (if applicable)) must be obtained and reviewed prior to enrollment.

1. *Within 7 days prior to the procedure*

- a) A laboratory panel including: a white blood cell count (WBC), platelet count, and creatinine.
- b) A pregnancy test (serum or urine) for women of childbearing potential
- c) A 12-lead ECG

2. *Within 72 hours prior to the procedure*

- a) Creatine kinase and troponin

Note: If it is not standard hospital practice to measure CK values, CK-MB values are sufficient. All subjects should have Troponin values.

RESOLUTE Onyx 2.0 mm Clinical Study
CONFIDENTIAL - May not be reproduced without written permission from Medtronic

Table 3: Schedule of Treatments and Assessments

Event	Index Hospitalization				Follow-up Assessments				
	Screening/Pre-Procedure		Proced.	Post-Proced. ¹	30 Day	6 Month	12 Month	13 Month	24, 36 Months
	Screen	Prior to procedure within:			Subject Contact ²	Subject Contact ² or Clinic Visit ⁵	Subject Contact ²	Clinic Visit	Subject Contact ²
7 days		72 hours							
Informed Consent signed	X								
Medical and cardiac history	X								
Angina status	X			X	X	X	X	X	X
Pregnancy test ³		X							
Creatinine		X							
WBC with Plts		X							
12 lead ECG		X		X Within 24 hours					
CK ⁶ and Troponin			X	X 1st: >3hrs 2nd: >4 hrs after 1st, < 24 hrs					
MPI ⁵						X			
QCA			X					X ⁴	
AE monitoring			X	X	X	X	X	X	X SAEs only
Antiplatelet medications	X Within 24 hours			X	X	X	X	X	X

1. End of procedure is defined as removal of the guide catheter

2. Subject contact includes phone call, email or clinic visit

3. For women of childbearing potential only

4. 2.0 mm Angio Subset only

5. Clinical visit for MPI assessment required for subjects that received an MPI at baseline and agree to do a follow-up MPI

6. If it is not standard hospital practice to measure CK values, CK-MB values are sufficient. All subjects should have Troponin values.

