5.6 Follow-Up Requirements

5.6.1 Follow-up General Requirements

The general requirements for follow-up in this trial include:

1. Enrolled subjects who received a study stent will be followed for 3 years after the index procedure by authorized study staff at the investigational site. See [Table 6](#) for follow-up assessment requirements.
2. Subjects in the 2.0 mm Angio subset will return to the site where the procedure was performed for a 13-month clinic visit including an angiogram. Other follow-up contacts will be conducted by telephone, e-mail or clinical visit, unless an unscheduled clinic visit occurs during a follow-up window.
3. A missed follow-up assessment will be documented by the investigator and reported in the eCRF, including the reason for the missed follow-up assessment in the subject's file.
4. Clinical assessments (e.g., angina status, use of antiplatelet medication, new and ongoing adverse events; medical, surgical or dental procedures and the interruption, if any, to antiplatelet therapy) must be performed at each follow-up contact and prior to any interventional procedure (e.g., angiography, PCI) during the 3-year follow-up period.
5. Documentation of referring physicians, general practitioners, cardiologists and family members should be noted to facilitate continued ability to contact a study subject. Any planned long absences by the subject from the area should also be noted.
6. Angiography should be performed for any post-procedure clinical event (e.g., MI) to determine if the event is attributable to the target vessel(s) or a non-target vessel.

The schedule and method for follow-up contacts and windows for each contact is tabled below.

Table 6: Follow-up Contact Requirements

Follow-up Interval	Window	Method*
30 days	± 5 days	Contact
6 months	±14 days	Contact/Clinic Visit**
12 months	± 30 days	Contact
12 month Clinical Follow up must occur at least 1 day prior to the 13 month Angiographic Follow up		
13 months (2.0 mm Angio subset)	± 14 days	Clinic Visit (with Angio)
2 Year	± 30 days	Contact
3 Year	± 30 days	Contact

*Subject contact includes phone call, email or clinic visit

**Clinic visit for subjects with baseline MPI performed, otherwise subject contact visit

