8.2 Serious Adverse Events

8.2.1 Definition

A serious adverse event (SAE) is defined as an adverse medical occurrence that:

- a) led to death
- OR
- b) led to a serious deterioration in the health of a subject that either resulted in
 - 1) a life-threatening illness or injury, or

RESOLUTE Onyx 2.0 mm Clinical Study**CONFIDENTIAL - May not be reproduced without written permission from Medtronic**

- 2) a permanent impairment of a body structure or a body function, or
- 3) in-patient or prolonged hospitalization, or
- 4) medical or surgical intervention to prevent life-threatening illness or injury or permanent impairment to body structure or a body function

OR

- c) led to fetal distress, fetal death or a congenital abnormality or birth defect.

Note: Planned hospitalization for a pre-existing or a procedure required by the protocol without serious deterioration in health, is not considered a serious adverse event.

The secondary endpoint, MACE (death, Q- or non-Q-wave myocardial infarction, emergent CABG or clinically-driven repeat target lesion revascularization by percutaneous or surgical method), is considered "serious" by this definition.

All serious adverse events (SAE) will be reported for the duration of the trial.

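### Protocol 8.1.2 ends non-serious AE reporting at 12 months, while Table 3 schedules unrestricted AE monitoring at the 13-month angiographic visit; the two need to be reconciled

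*Protocol*

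**What the plan says.** Four places in the Protocol bear on this.

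- **Section 8.1.2** requires recording and eCRF reporting of "All non-serious AEs occurring from the time of index procedure through 12 months post-procedure". It makes no exception for the angiographic subset.
- **Section 8.2.1** sets a different period for serious events: "All serious adverse events (SAE) will be reported for the duration of the trial".
- **Table 3 (section 5.2)** has a row labelled "AE monitoring". It carries a plain mark at every column from the procedure through the 13-month clinic visit. The restriction to serious events appears only in the combined 24- and 36-month column.
- **Section 5.6.1 item 4** lists "new and ongoing adverse events" among the assessments due at each follow-up contact and before any interventional procedure over the 3 years. It has no cut-off at 12 months and no limit to serious events.

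The 13-month visit exists for the angiographic subset. Section 4.0 says: "At least 20 subjects will be enrolled to receive an angiographic follow up at 13 months". Section 5.6.1 item 2 has these subjects return to the site "for a 13-month clinic visit including an angiogram". Table 6 fixes the order of the two visits: "12 month Clinical Follow up must occur at least 1 day prior to the 13 month Angiographic Follow up". Tables 8 and 10 give submission deadlines for AEs but no end date for collection.

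**The concern.** The reporting duty for non-serious AEs ends about a month before an invasive test that the protocol schedules for a subset of subjects. Section 6.2.3 lists access-site pain, haematoma or haemorrhage and allergic reaction to contrast among the risks of diagnostic procedures, angiography included. The AE definition in 8.1.1 covers events related to the procedures involved. Many such events would not meet the definition of serious.

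A site that works from 8.1.2 has no duty to report them. A site that works from Table 3 or 5.6.1 item 4 would collect them. At stake is the completeness and consistency of the minor-harm record for a test performed because the trial asks for it.

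**Working it through.** **Step 1: reproduce the protocol's visit dates.** The inputs are the example implant date of 5 December 2014 (Table 7), the anniversary rule (section 5.6.2) and the windows in Table 6 (±30 days at 12 months, ±14 days at 13 months).

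- 12 months: 5 Dec 2015 = day 365; window 365 ± 30 = days 335 to 395 (5 Nov 2015 to 4 Jan 2016).
- 13 months: 5 Jan 2016 = day 396; window 396 ± 14 = days 382 to 410 (22 Dec 2015 to 19 Jan 2016).

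These dates match Table 7.

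**Step 2: compare the angiogram with the 8.1.2 period.** The earliest in-window angiogram is on day 382, and 382 − 365 = 17 days after the 12-month date. Read as written, 8.1.2 covers no in-window angiogram.

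A looser reading would let 12 months run to the end of the 12-month visit window, day 395. Angiograms on days 382 to 395 would then be inside the period and those on days 396 to 410 outside it. The 13-month target date itself (day 396) would still be uncovered.

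SAP Appendix II counts days differently: 360 ± 30 gives 330 to 390, and 390 ± 14 gives 376 to 404. Under the looser reading, days 376 to 390 would be covered and days 391 to 404 would not. The result is the same in kind.

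**Step 3: look for a later collection point.** The next scheduled contact is at 2 years, 5 Dec 2016 = day 731, which is 731 − 396 = 335 days after the 13-month target. Table 3 limits that contact to serious events. So even under Table 3, a non-serious event that appears after the subject leaves the 13-month visit has no scheduled collection point. Only 5.6.1 item 4 would pick it up, and at 24 and 36 months that item itself conflicts with Table 3.

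**Step 4: set the instructions side by side for a non-serious event caused by the 13-month angiogram.**

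| Source | Instruction |
|---|---|
| 8.1.2 | Outside the reporting period |
| Table 3, 13 months | AE monitoring, unrestricted |
| 5.6.1 item 4 | Assess new and ongoing AEs at each contact |
| Table 3, 24 and 36 months | Serious events only |
| Tables 8 and 10 | Deadline given, no end date |

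No section states which of these governs.

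**Step 5: scale.** The documents give no complication rate, so the rate p is an assumption. With n = 20, the minimum subset size, and independent events, P(at least one) = 1 − (1 − p)^20:

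- p = 1%: 1 − 0.99^20 = 0.18
- p = 2%: 1 − 0.98^20 = 0.33
- p = 5%: 1 − 0.95^20 = 0.64
- p = 10%: 1 − 0.90^20 = 0.88

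The answer depends almost wholly on the assumed rate. It shows only that such an event is plausible in a subset of this size.

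**The case against.** A reader might infer from 8.1.2 that non-serious harms of the 13-month angiogram will go unreported. The documents do not support that. Table 3 marks AE monitoring at the visit, 5.6.1 item 4 requires new and ongoing AEs to be assessed there, and section 9.11.2 lists adverse events among the source records. A site following those instructions would record the event. The defect is a set of conflicting instructions, not a demonstrated gap in collection.

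Other parts of the case against also stand:

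- The more consequential harms are covered. Serious events, including in-patient or prolonged hospitalisation, are reported throughout, and MACE is classed as serious (8.2.1). What is left is minor.
- Ending non-serious AE reporting at 12 months is not an error in itself. The problem is that it disagrees with the schedule.
- No single figure from step 5, such as 64%, should be read as an estimate for this trial.
- The case report forms (Appendix 5) are supplied separately and may prompt for AEs at 13 months. That variation between sites will occur is therefore a possibility, not a finding.
- Section 8.1.2 names relationship to device as the causality item, so extending the period would not by itself attribute an event to the angiogram.

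None of this removes the conflict. A prompt on a form would help in practice, but 8.1.2 would still place the event outside the reporting period.

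**Conclusion.** The inconsistency is real but minor. Under 8.1.2 as written, non-serious events from the protocol-scheduled 13-month angiogram are not required to be reported, while Table 3 and 5.6.1 item 4 direct that AEs be assessed at that visit. The record for at least 20 subjects may be incomplete or may differ between sites.

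A reader might also suspect that the trial's main conclusion is affected. It is not: the primary endpoint is TLF at 12 months, and the 13-month angiogram must follow the 12-month contact.

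The conclusion rests on reading the 8.1.2 limit as the 12-month anniversary. Extending it to the end of the visit window narrows the mismatch but does not close it. The scale figures rest on assumed rates of 1% to 10%, on independent events and on exactly 20 subjects; a larger subset would raise them.

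**What to change.** Amend 8.1.2 so that, for angiographic-subset subjects, non-serious AEs are reported through the 13-month angiogram visit and a short period after it, with the length stated by the sponsor. Keep 12 months for all other subjects. This brings 8.1.2 into line with the 13-month column of Table 3, and the stated period after the visit covers events that appear once the subject has left.

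In the same amendment, reconcile 5.6.1 item 4 with the serious-only entry in Table 3 at 24 and 36 months, so that one rule applies to late contacts. If the sponsor instead intends to collect only serious events at 13 months, Table 3 must be corrected to say so, and the reduced collection around the angiogram should be a stated decision.

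The cost is one sentence in 8.1.2, a wording change in 5.6.1 or Table 3, and slight extra AE entry for about 20 subjects.

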8.2 Serious Adverse Events

8.2.1 Definition

A serious adverse event (SAE) is defined as an adverse medical occurrence that:

- a) led to death
- OR
- b) led to a serious deterioration in the health of a subject that either resulted in
 - 1) a life-threatening illness or injury, or

RESOLUTE Onyx 2.0 mm Clinical Study**CONFIDENTIAL - May not be reproduced without written permission from Medtronic**

- 2) a permanent impairment of a body structure or a body function, or
- 3) in-patient or prolonged hospitalization, or
- 4) medical or surgical intervention to prevent life-threatening illness or injury or permanent impairment to body structure or a body function

OR

- c) led to fetal distress, fetal death or a congenital abnormality or birth defect.

Note: Planned hospitalization for a pre-existing or a procedure required by the protocol without serious deterioration in health, is not considered a serious adverse event.

The secondary endpoint, MACE (death, Q- or non-Q-wave myocardial infarction, emergent CABG or clinically-driven repeat target lesion revascularization by percutaneous or surgical method), is considered "serious" by this definition.

All serious adverse events (SAE) will be reported for the duration of the trial.

8.2.2 Reporting Requirements

Any AE meeting any of the above criteria for SAE occurring at any time during the trial must be reported by the Investigator or designee, within 3 days after any study site personnel active on the Delegation of Authority first learns of the event. The SAE must also be reported to the IRB per the institution's policy for reporting SAEs.

8.3 Unanticipated Adverse Device Effects

8.3.1 Definition

An unanticipated adverse device effect (UADE) is defined as any serious adverse effect on health or safety or any life-threatening problem or death caused by, or associated with, a device, if that effect, problem, or death was not previously identified in nature, severity, or degree of incidence in the investigational plan or application (including a supplementary plan or application), or any other unanticipated serious problem associated with a device that relates to the rights, safety, or welfare of subjects.

